| Other non- hematologic adverse events | Non-hematologic Grade 3 or 4 | Auranofin Sirolimus | Delay therapy until severity decreases to grade 0-1 and decrease dose by one level; discontinue treatment if toxicity persists beyond 14 days or if subject is already at dose level -2 and go to event monitoring phase per Section 18 |

^{*} Located at http://ctep.cancer.gov/protocolDevelopment/electronic applications.ctc.htm

NOTE: Adverse events requiring a dose-reduction step for any or all drugs beyond the two dose-reduction steps (levels -1 and -2) will result in the patient coming off study.

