13.0 Treatment/Follow-up Decision at Evaluation of Patient

- 13.1 Patients who are CR, PR, or SD will continue treatment per protocol.
- Patients who develop PD while receiving therapy will go to the event-monitoring phase.
- Patients who go off protocol treatment for reasons other than PD will go to the event-monitoring phase per Section 18.0.

- 13.4 Patients who develop PD in the CNS only should receive resection and/or brain radiationand continue treatment on study after completion of CNS treatment.
- Patients who develop non-CNS PD at any time should go to event monitoring. These patients should be treated with alternative chemotherapy if their clinical status is good enough to allow further therapy.
- 13.6 A patient is deemed *ineligible* if after registration, it is determined that at the time of registration, the patient did not satisfy each and every eligibility criteria for study entry. The patient may continue treatment off-protocol at the discretion of the physician as long as there are no safety concerns, and the patient was properly registered. The patient will go directly to the event-monitoring phase of the study (or off study, if applicable).
 - If the patient received treatment, all data up until the point of confirmation of ineligibility must be submitted. Event monitoring will be required per Section
 - 18.0 of the protocol.
 - If the patient never received treatment, on-study material must be submitted. Event monitoring will be required per Section 18.0 of the protocol.
- 13.7 A patient is deemed a *major violation*, if protocol requirements regarding treatment in cycle 1 of the initial therapy are severely violated that evaluability for primary end point is questionable. All data up until the point of confirmation of a major violation must be submitted. The patient will go directly to the event-monitoring phase of the study. The patient may continue treatment off-protocol at the discretion of the physician as long as there are no safety concerns, and the patient was properly registered. Event monitoring will be required per Section 18.0 of the protocol.
- 13. 8 A patient is deemed a *cancel* if he/she is removed from the study for any reason before any study treatment is given. On-study material and the End of Active Treatment/Cancel Notification Form must be submitted. No further data submission is necessary.

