16.3 Phase II Design and Analysis

16.31 Primary Endpoint: The primary endpoint of this trial is the 4-month progression-free survival rate. Throughout Section 16.0, "4-month progression-free survivor" will be considered synonymous with "success", unless otherwise specified. A patient is considered to be a 4-month progression-free survivor if the patient is 4 months from registration without a documentation of disease progression (note, the patient need not be on study treatment at 4 months to be considered a success). All patients meeting the eligibility criteria who have signed a consent form and have initiated treatment will be evaluable for the primary endpoint.

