16.4 Statistical Design

16.41 Decision Rule: The largest success proportion where the proposed treatment regimen would be considered ineffective in this population is 35%, and the smallest success proportion that would warrant subsequent studies with the proposed regimen in this patient population is 55%. The following one-stage design based on properties of the binomial distribution uses 37 patients to test the null hypothesis that the true success proportion in a given patient population is at most 35%.

The null 4-month progression-free survival rate of 35% is based on Figure

2 of Scagliotti et al (2008). In the subgroup of patients with squamous cell carcinoma on the cisplatin / gemcitabine arm, approximately 65% of patients were progression-free 4 months after randomization (i.e., at or near completion of first-line therapy). Four months subsequent to this time point, the PFS rate was approximately 25%. Thus, among those who were progression-free at or near completion of first-line therapy, the subsequent 4-month PFS rate for patients receiving no maintenance therapy following first-line cisplatin / gemcitabine is approximately 35% ($\approx 0.25/0.65$).

Enter 37 patients into the study. If 16 or fewer successes are observed in the first 37 evaluable patients, we may consider this regimen ineffective in this patient population. If 17 or more successes are observed in the first 37 evaluable patients, we may recommend further testing of this regimen in subsequent studies in this population.

- 16.411 Over Accrual: If more than the target number of patients are accrued, the additional patients will not be used to evaluate the stopping rule or used in any decision making process. Analyses involving over accrued patients is discussed in Section 16.34.
- 16.42 Power and Significance Level: Assuming that the number of successes is binomially distributed, the significance level is ≤0.12 and the probability of declaring that this regimen warrants further studies (i.e., statistical power) under various success proportions can be tabulated as a function of the true success proportion as shown in the following table.

| If the true success proportion is | 0.35 | 0.40 | 0.45 | 0.50 | 0.55 |
|--|------|------|------|------|------|
| then the probability of declaring that the regimen warrants further studies is | 0.11 | 0.28 | 0.52 | 0.74 | 0.90 |

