16.51 Primary Endpoint

- 16.511 Definition: The primary endpoint of this trial is the proportion of 4-month progression-free survivors as defined in Section 16.31.
- 16.512 Estimation: The proportion of successes will be estimated by the number of successes divided by the total number of evaluable patients. Confidence intervals for the true success proportion will

be calculated using the properties of the binomial distribution. Additionally, if some patients are lost to follow-up not having been observed for at least 4 months, an estimate and confidence interval for the 4-month progression-free survival rate incorporating censoring will be computed using the method of Kaplan-Meier (1958).

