16.52 Definitions and Analyses of Secondary, Exploratory, and Correlative Endpoints

Survival time is defined as the time from registration to death due to any cause. The distribution of survival time will be estimated using the method of Kaplan-Meier (1958).

Progression-free survival time is defined as the time from registration to the earliest date of documentation of disease progression. If a patient dies without a documentation of disease progression the patient will be considered to have had disease progression at the time of their death. In the case of a patient starting treatment and then never returning for any evaluations, the patient will be censored for progression 1 day post-registration. The distribution of progression-free survival time will be estimated using the method of Kaplan-Meier (1958).

A response is defined to be either a CR or PR noted as the objective status. As response rate is a secondary endpoint, confirmation is no longer required per RECIST v1.1. The overall response rate will be estimated in the subset of patients with measureable disease by the number of responses in evaluable patients with measurable disease divided by the total number of evaluable patients with measureable disease. The appropriate confidence interval will be calculated based on the binomial distribution.

Duration of response is defined for all evaluable patients with measurable disease who have achieved a response as the date at which the patient's earliest best objective status is first noted to be either a CR or PR to the earliest date progression is documented. If a patient dies subsequent to the response without a documentation of disease progression, the patient will be considered to have had disease progression at the time of their death. In the case of a patient failing to return for evaluations before a documentation of disease progression, the patient will be censored for progression on day 1 post response or the date of last evaluation (whichever one occurs later). The distribution of

duration of response will be estimated using the method of Kaplan-Meier (1958).

Translational analyses: Given the small sample size, all translational analyses are considered exploratory and no adjustment for multiplicity will be employed. One-sided p-values

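### As worded, the success definition in 16.31 lets a patient lost or withdrawn before 4 months count as a success in the 17-of-37 rule, and it does not name death as a failure

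*Combined protocol and SAP*

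**What the plan says.** The primary endpoint is set in 16.31: "A patient is considered to be a 4-month progression-free survivor if the patient is 4 months from registration without a documentation of disease progression". The same section adds that a success need not still be on treatment, and that every eligible patient who consented and started treatment is evaluable. Section 16.511 only refers back to 16.31. Section 16.512 estimates the success proportion as successes over all evaluable patients. It then adds a Kaplan-Meier estimate with censoring "if some patients are lost to follow-up not having been observed for at least 4 months".

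Section 16.41 bases the decision on the count alone: 17 or more successes in the first 37 evaluable patients supports further study, and 16 or fewer does not.

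Section 16.52 defines progression-free survival time among the secondary endpoints. There, death is covered: "If a patient dies without a documentation of disease progression the patient will be considered to have had disease progression". A patient who starts treatment and never comes back is handled differently: "the patient will be censored for progression 1 day post-registration". Section 16.31 cites neither rule.

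On stopping for toxicity, the note under the 8.2 table says that needing a reduction beyond level -2 "will result in the patient coming off study". The table rows for neutrophils, platelets and other non-hematologic events send a patient already at level -2 to event monitoring. Section 13 has the same general rule: "Patients who go off protocol treatment for reasons other than PD will go to the event-monitoring phase per Section 18.0". The paragraph on ineligible patients (13.6) mentions the "event-monitoring phase of the study (or off study, if applicable"), so the protocol treats these as two different states.

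**The concern.** The definition has two conditions: time elapsed since registration, and no progression on record. It does not ask that the patient be alive, followed or assessed at 4 months. A patient who withdraws at month 1 without progression on record meets both conditions at month 4 and remains in the denominator. Absence of information is then scored as benefit.

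This matters because the trial has one arm and a fixed cut-off. A few patients of unknown status can decide the result, and the reading chosen moves the error rates in opposite directions. If the rule is settled after the data are seen, the stated error rates no longer describe the test.

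**Working it through.** **Inputs from 16.41 and 16.42.** Null rate p0 = 0.35 ("The largest success proportion where the proposed treatment regimen would be considered ineffective in this population is 35" per cent); alternative p1 = 0.55; n = 37; cut-off 17 successes; significance level at most 0.12. The number k of patients whose 4-month status is unknown is not in the documents. I assume k = 1 to 4.

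**Step 1: the plan's own figures.** P(X ≥ 17) with X ~ Bin(37, p) gives 0.1118, 0.2819, 0.5175, 0.7443 and 0.8981 at p = 0.35, 0.40, 0.45, 0.50 and 0.55. The table in 16.42 has 0.11, 0.28, 0.52, 0.74 and 0.90. It reproduces, and 0.1118 is within 0.12.

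**Step 2: the k patients scored as successes (16.31 read literally).** The other 37 − k patients need only 17 − k successes, so the probability of a positive result is P(X ≥ 17 − k), X ~ Bin(37 − k, p). For k = 1 at p = 0.35 this is P(X ≥ 16), X ~ Bin(36, 0.35) = 0.155.

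**Step 3: the k patients scored as non-successes.** The other 37 − k must supply all 17: P(X ≥ 17), X ~ Bin(37 − k, p).

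| k | Type I error, scored as success | Type I error, scored as non-success | Power at 0.55, scored as non-success |
|---|---|---|---|
| 0 | 0.112 | 0.112 | 0.898 |
| 1 | 0.155 | 0.088 | 0.865 |
| 2 | 0.211 | 0.068 | 0.825 |
| 3 | 0.279 | 0.051 | 0.776 |
| 4 | 0.359 | 0.038 | 0.719 |

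**Step 4: the same as a loss rate.** Let each patient be lost with probability d, independently of outcome. Scored as success, the effective null rate is p0(1 − d) + d. For d = 0.05 it is 0.35 × 0.95 + 0.05 = 0.3825, with type I error 0.212. For d = 0.10 it is 0.415, with type I error 0.349. Scored as non-success, d = 0.10 gives an effective null rate of 0.35 × 0.90 = 0.315 (type I error 0.046) and an effective alternative of 0.55 × 0.90 = 0.495 (power 0.724).

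**Step 5: can 4-month status be missing?** Tumor assessment follows treatment cycles (Section 4.0, footnote 2) or an 8-week interval (11.1). After treatment stops for a reason other than progression, Section 18.0 requires an event-monitoring form every 3 months until progression; it names no scan at 4 months. Section 16.512 itself provides for patients lost before 4 months. The over-accrual in 16.12 is for cancellation, ineligibility and major violations, and loss to follow-up is not listed.

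**The case against.** The best defence is that being 4 months from registration means observed to 4 months. Section 16.13 times the final analysis by 4 months' observation of the last patient, 16.6 defines primary completion by follow-up of that length, and 16.512 separates out those not observed so long. That reading is possible, so success by default is what the words literally give rather than a declared intention. But under it the lost patient is still evaluable, still in the denominator, and has no stated place in the count. The same sentence is needed.

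The plan also has safeguards. Patients who stop for toxicity are generally still followed, symptomatic deterioration is reported as progression (11.45), and a severe cycle 1 violation may put evaluability in question (13.7). These reduce the number of unknowns; they do not say how to score those that remain.

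Three stronger readings are tempting and are not supported:

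- A reader might infer that 16.31 contradicts 16.52 on death. It is silent. It calls a success a survivor, which implies being alive. What is missing is an explicit clause or a cross-reference.
- A reader might infer that the count and the Kaplan-Meier estimate could give opposite decisions. With 3 lost and 16 successes among the other 34, for instance, 16/37 = 43% is below the cut-off of 17/37 = 46%, while 16/34 = 47% is above it. But 16.512 introduces Kaplan-Meier only as an addition, and 16.41 gives it no part in the decision.
- A reader might infer that the 8.2 note settles that some toxicity patients leave the study. The table above it and Section 13 say otherwise, so this is an unresolved conflict.

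**Conclusion.** The point stands as a defect in the primary endpoint definition. Taken literally, 16.31 turns a patient of unknown status into a success; on the kinder reading, the scoring is undefined. The design arithmetic in 16.42 is correct. What is at risk is whether the stated error rates apply to the count actually made.

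One patient scored as a success by default is enough to break the 0.12 limit (0.155), and four bring type I error to 0.359. These figures assume k, since the documents give no loss rate, and assume that the other 37 − k patients each succeed with probability 0.35. If every patient's status at 4 months is known and deaths are counted as failures, there is no effect.

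The omission of death is smaller, because the sense of the endpoint is clear, but it belongs in the same correction. The conflict over the 8.2 note bears on this point because it leaves unclear whether progression and survival status would be collected for those patients.

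**What to change.** In 16.31, state that:

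- a success must be known to be alive and progression-free at 4 months after registration;
- death from any cause before then is a failure;
- an evaluable patient whose 4-month status is not known stays among the 37 as a non-success.

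In 16.512, label the Kaplan-Meier estimate a sensitivity analysis with no role in the 17-of-37 decision.

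Separately, ask the sponsor to reconcile the note under 8.2 with the 8.2 table rows and Section 13, so that progression and survival status to 4 months is available for these patients. Which of those rules should prevail is for the sponsor to decide.

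The statistical change is wording only and adds no patients. Its price is a more conservative test: with 1, 2, 3 or 4 patients of unknown status, power at 0.55 falls from 0.90 to 0.87, 0.83, 0.78 or 0.72, while type I error falls from 0.11 to 0.09, 0.07, 0.05 or 0.04. That loss is a reason to obtain 4-month status for every patient.

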16.4 Statistical Design

16.41 Decision Rule: The largest success proportion where the proposed treatment regimen would be considered ineffective in this population is 35%, and the smallest success proportion that would warrant subsequent studies with the proposed regimen in this patient population is 55%. The following one-stage design based on properties of the binomial distribution uses 37 patients to test the null hypothesis that the true success proportion in a given patient population is at most 35%.

The null 4-month progression-free survival rate of 35% is based on Figure

2 of Scagliotti et al (2008). In the subgroup of patients with squamous cell carcinoma on the cisplatin / gemcitabine arm, approximately 65% of patients were progression-free 4 months after randomization (i.e., at or near completion of first-line therapy). Four months subsequent to this time point, the PFS rate was approximately 25%. Thus, among those who were progression-free at or near completion of first-line therapy, the subsequent 4-month PFS rate for patients receiving no maintenance therapy following first-line cisplatin / gemcitabine is approximately 35% ($\approx 0.25/0.65$).

Enter 37 patients into the study. If 16 or fewer successes are observed in the first 37 evaluable patients, we may consider this regimen ineffective in this patient population. If 17 or more successes are observed in the first 37 evaluable patients, we may recommend further testing of this regimen in subsequent studies in this population.

- 16.411 Over Accrual: If more than the target number of patients are accrued, the additional patients will not be used to evaluate the stopping rule or used in any decision making process. Analyses involving over accrued patients is discussed in Section 16.34.
- 16.42 Power and Significance Level: Assuming that the number of successes is binomially distributed, the significance level is ≤0.12 and the probability of declaring that this regimen warrants further studies (i.e., statistical power) under various success proportions can be tabulated as a function of the true success proportion as shown in the following table.

| If the true success proportion is | 0.35 | 0.40 | 0.45 | 0.50 | 0.55 |
|--|------|------|------|------|------|
| then the probability of declaring that the regimen warrants further studies is | 0.11 | 0.28 | 0.52 | 0.74 | 0.90 |

- 16.43 Other Considerations: Adverse events, quality/duration of response, and patterns of treatment failure observed in this study, as well as scientific discoveries or changes in standard care will be taken into account in any decision to terminate the study.
- Analysis Plan: The analysis for this trial will commence at planned timepoints and at the time the patients have become evaluable for the primary endpoint. Such a decision will be made by the Statistician and Study Chair, in accordance with Mayo Clinic Cancer Center (MCCC) Standard Operating Proceedures, availability of data for secondary endpoints (e.g., laboratory correlates), and the level of data maturity.

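### The 35% null is a wrong quotient: the plan's own inputs (0.25/0.65) give 38.5%, so the false-positive rate against the cited benchmark is 0.22, not 0.11

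*Combined protocol and SAP*

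**What the plan says.** Section 16.41 (Decision Rule) sets the two design proportions: "The largest success proportion where the proposed treatment regimen would be considered ineffective in this population is 35" per cent, and "the smallest success proportion that would warrant subsequent studies with the proposed regimen in this patient population is 55" per cent.

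It then explains where the lower figure comes from: "The null 4-month progression-free survival rate of 35% is based on Figure" 2 of a cited phase III first-line trial, squamous subgroup, cisplatin/gemcitabine arm. Two values are read from that curve. First, "approximately 65% of patients were progression-free 4 months after randomization". Second, "Four months subsequent to this time point, the PFS rate was approximately 25" per cent. From these the plan concludes that "the subsequent 4-month PFS rate for patients receiving no maintenance therapy following first-line cisplatin / gemcitabine is approximately 35" per cent, and it prints the division 0.25/0.65 beside that result.

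The decision rule follows. The regimen may be recommended for further testing "If 17 or more successes are observed in the first 37 evaluable patients". Section 16.42 adds: "Assuming that the number of successes is binomially distributed, the significance level is ≤0.12". Its table gives the probability of a positive decision as 0.11, 0.28, 0.52, 0.74 and 0.90 at true success proportions of 0.35, 0.40, 0.45, 0.50 and 0.55.

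**The concern.** The derivation is a conditional probability: among patients still progression-free at 4 months, the share still progression-free at 8 months. That is the right form for the quantity the plan wants, but the printed division does not equal the printed answer. The documents offer no other reason for choosing 35%.

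This matters because the phase II part is a single-arm, one-stage design. The null proportion takes the place of a control group, and the stated significance level describes the decision only if the null matches the benchmark it is said to represent. If the benchmark is higher than 35%, a regimen that does no better than no maintenance therapy passes more often than the reader is told. Section 16.52 looks ahead to a phase III study if this trial is supportive, so the false-positive rate bears on a real decision.

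**Working it through.** **Inputs** (all from Sections 16.41 and 16.42)

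- Progression-free at 4 months: S(4) ≈ 0.65
- Progression-free at 8 months: S(8) ≈ 0.25
- Null used: 0.35; alternative: 0.55
- n = 37 evaluable; positive decision if X ≥ 17

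**Step 1. Reproduce the plan's figures.** With X ~ Binomial(37, p), the exact upper tail P(X ≥ 17) is:

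| True p | Plan's table | Recomputed |
|---|---|---|
| 0.35 | 0.11 | 0.1118 |
| 0.40 | 0.28 | 0.2819 |
| 0.45 | 0.52 | 0.5175 |
| 0.50 | 0.74 | 0.7443 |
| 0.55 | 0.90 | 0.8981 |

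Every entry agrees. Section 16.42 is correct for a 35% null.

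**Step 2. Recompute the benchmark.** S(8)/S(4) = 0.25/0.65 = 0.3846, or 38.5%. This could be rounded to 38%, or coarsely to 40%, but not to 35%.

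**Step 3. Apply the unchanged rule at that benchmark.** P(X ≥ 17 | n = 37, p = 0.3846) = 0.2202. The ratio to the value at 0.35 is 0.2202/0.1118 = 1.97. The plan's own table brackets this result: 38.5% lies between 0.35 (0.11) and 0.40 (0.28).

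**Step 4. Find how high the null may be.** P(X ≥ 17 | n = 37, p) reaches 0.12 at p = 0.353. The printed quotient is about 3 points above that. To obtain exactly 35%, the inputs would have to be 0.2275 over 0.65 (0.35 × 0.65 = 0.2275) or 0.25 over 0.714 (0.25/0.35 = 0.714).

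**Step 5. Allow for reading error.** The curve is not available here, so the size of the error is an assumption.

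| S(8)/S(4) | Quotient | P(X ≥ 17) |
|---|---|---|
| 0.24/0.66 (one point each) | 0.364 | 0.149 |
| 0.25/0.65 (as printed) | 0.385 | 0.220 |
| 0.26/0.64 (one point each) | 0.406 | 0.309 |
| 0.23/0.67 (two points each) | 0.343 | 0.096 |
| 0.27/0.63 (two points each) | 0.429 | 0.413 |

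**Step 6. Look for a rule that fits a null of 0.3846.**

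| n | Cut-off | Alpha at 0.3846 | Power at 0.55 |
|---|---|---|---|
| 37 | ≥ 17 | 0.220 | 0.898 |
| 37 | ≥ 18 | 0.135 | 0.827 |
| 37 | ≥ 19 | 0.076 | 0.730 |
| 55 | ≥ 26 | 0.115 | 0.901 |

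With 37 patients, 19 is the first cut-off that meets the 0.12 ceiling. Its power at 58.5%, which would keep the 20-point gap between null and alternative, is 0.853. The smallest sample that meets alpha ≤ 0.12 and power ≥ 0.90 at 55% is 55 evaluable patients.

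**The case against.** The strongest reply is that 35% is declared in its own right as the largest uninteresting success rate, and that the error rate and power are correct for it. On this view the slip lies in a supporting sentence, and 0.22 is simply the rejection probability at another proportion. The first part is true: nothing in the Section 16.42 table is miscalculated. But the plan says that the 35% is based on this curve and gives no other ground for it, so the declared null and its only justification disagree.

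A second reply is that both inputs are approximate, and that 35% may be the intended figure with an input misprinted or coarsely rounded. This cannot be excluded from the documents. A two-point error in each reading, in the favourable direction, brings the false-positive rate to 0.096; in the other direction it goes to 0.413. What stands is that the source should be checked before the null is changed. It does not rescue the text, because readings that give 35% are not the ones printed, and one or the other must then be corrected.

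A third reply is that the benchmark is only a proxy. It describes squamous patients still progression-free near the end of first-line therapy, whereas Section 3.1 admits squamous, Ras-mutated adenocarcinoma and small cell patients with no acceptable standard options. That is fair, and it means 0.22 should be described as the rate against the cited benchmark, not as the trial's actual false-positive rate. Whether the benchmark suits this population is a separate question and does not make the division right.

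Finally, the table already shows 0.28 at a true rate of 0.40, so the steepness of the rule near the null is visible. A reader would still take 0.11 as the error rate against the cited control.

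**Conclusion.** The concern holds. The plan's printed inputs give a benchmark of 38.5%, and at that value the rule of 17 or more in 37 yields a positive decision with probability 0.22. This is about twice the tabulated 0.11 and above the stated ceiling of 0.12. The result assumes binomial counts, as the plan does, and the values 0.25 and 0.65 as printed. Under a one-point reading error in each input, in opposite directions, the rate stays above the ceiling, at 0.149 to 0.309; it can fall below 0.12 only if the readings differ further from those the plan reports. Because this null is the sole comparator for the primary endpoint, the correction is needed before the decision rule is relied on.

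**What to change.** Re-read the two values from the source curve first. If 0.65 and 0.25 stand, correct the null in Section 16.41 to about 38.5% and recompute Sections 16.41 and 16.42 with n kept at 37. To honour the ceiling of 0.12, require at least 19 successes and state alpha as 0.076 and power as 0.73 at 55%, or 0.85 if the alternative is moved to 58.5%. If the inputs turn out to be wrong, correct them and derive the null from the corrected values. If 35% is to be kept on other grounds, state those grounds and remove the reliance on 0.25/0.65.

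At minimum, if the cut-off of 17 is retained, add a column at 0.385 to the Section 16.42 table and state that the false-positive rate against the cited benchmark is 0.22.

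The minimum change costs only wording. Moving the cut-off to 19 needs no further patients but lowers power at 55% from 0.90 to 0.73. Keeping both alpha at or below 0.12 and power of at least 0.90 at 55% would need 55 evaluable patients with a cut-off of 26, which is 18 more than planned (55 − 37).
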